3.5 Measured Study Endpoints

The biomarker endpoints used for the interim biomarker analyses are specific for each drug based on mechanism of action. These are listed in each drug-specific appendix and/or drug-specific SAP appendix. The designation of primary, secondary, and exploratory endpoints are also specific for each drug and are listed in the drug-specific appendices and/or drug-specific SAP appendices.

Note – measures and endpoints for completed drug arms can be found in prior protocol amendments and SAPs; the gantenerumab open label extension endpoints are in [Appendix 3](#). The E2814 measures and endpoints with concurrent lecanemab treatment are in [Appendix 4](#).

Additional outcome measures include comparisons between each drug and placebos and eligible DIAN-OBS participants for measures listed below if/as specified in the drug-specific SAP appendix.

Clinical Measures

Clinical measures to be obtained at the CRI Entry, baseline (V2), and annual visits for both the CRI period and treatment periods will be administered at a DIAN-TU site include:

- Clinical Dementia Rating™ (CDR), including Clinical Dementia Rating Sum of Boxes™ (CDR-SB) and clinician's diagnostic assessment
- Geriatric Depression Scale (GDS)
- Neuropsychiatric Inventory Questionnaire (NPI-Q)
- Functional Assessment Scale (FAS)
- Mini-Mental State Examination (MMSE)*

*In addition, the MMSE will be administered at the site or via home visits for secondary prevention population only by a DIAN-TU certified rater at the 26-week visit in between the annual visits, as specified in the CRI and drug-specific appendices.

Cognitive Measures

Cognitive batteries are defined in respective arm-specific appendices. Refer to the arm-specific *DIAN Trials Unit Cognition Core Procedures Manuals* for additional information. Refer to prior

amendments for details on the cognitive battery administered in completed or closed drug arm periods.

Cognitive Battery for Gantenerumab Open-Label Extension Period

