1.9.2 Open-Label Extension

Primary endpoints for the OLE include cerebral amyloid imaging using [¹¹C]PiB-PET as well as the safety and tolerability of treatment with gantenerumab at higher doses.

Additional study endpoints for the gantenerumab OLE will be specified in the gantenerumab-specific SAP. The objectives of the OLE are as follows:

- (i) To enable participants, who have committed as much as 4 to 7 years to the double-blind treatment period of the study, to continue or begin to receive gantenerumab, which improves critical markers of their progressive disease, following their participation in the longest placebo-controlled trial in DIAD;
- (ii) To determine if continued treatment with gantenerumab at its target dose can result in complete removal of brain amyloid;
- (iii) To investigate which non-amyloid related downstream biological measures (e.g. tau and markers of neurodegeneration) can be improved or normalized with complete removal of amyloid at different stages of disease;
- (iv) To investigate the relationship of these biological measures with cognitive and clinical findings; and
- (v) To assess the summation of gantenerumab's effect on biomarkers during the entire double-blind period and open label extension period, including the common close portion in which biomarkers were not assessed (i.e., from year 4 to 7).

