5.3. MODIFIED INTENT-TO-TREAT [mITT]

The mITT analysis populations include all enrolled mutation positive subjects who receive any treatment post-baseline and have at least one assessment for the analysis primary parameter (PiB-PET SUVR for final analysis, CDR Global for both the interim analysis and the final analysis) prior to the associated treatment period (as a baseline assessment) and a post-baseline assessment. For analysis of clinical/cognitive endpoints or non-PET biomarker endpoints, the mITT population identified based on CDR Global should be used.

Author: [REDACTED]

Version Number:

7

Version Date:

07Dec2023

[figure not shown]
Template No.: CS_TP_BS016 Revision 6

Reference: CS_WI_BS005

Effective Date: 02Dec2019

There will be three separate mITT populations:

1. OLE Gant mITT: Any subjects in the OLE meeting mITT criteria using OLE baseline (defined as the last assessment time for the analysis primary parameter prior to the first dose of OLE treatment) as the baseline reference point. Refer to figure below where the data contributing to the population is highlighted in yellow (and denoted with '(Tx)') for the OLE period, regardless of double-blind treatment, with controls (further described in [Section 5.4](#)) highlighted in green from both placebo double-blind only subjects and matched controls from DIAN-OBS.

2. OLE Gant All Gant exposure mITT: Any subjects treated with gantenerumab in both the DB and OLE who meet mITT criteria using DB baseline as the baseline reference point. Refer to figure below where the data contributing to the population is highlighted in yellow (and denoted with '(Tx)') for subjects treated with gantenerumab in both DB and

Author: [REDACTED]

Version Number:

7

Version Date:

[figure not shown]
07Dec2023

Template No.: CS_TP_BS016 Revision 6

Reference: CS_WI_BS005

Effective Date: 02Dec2019

OLE, with main set controls (further described in [Section 5.4](#)) highlighted in green from both placebo double-blind only subjects and matched controls from DIAN-OBS, and an additional set of extended controls (using DB and OLE baseline values for double-blind placebo subjects entering OLE) in a different shade of green to be added to the main set controls to form a second set of controls for the population.

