5.4.4. EXTENDED SET CONTROLS

The extended set controls are defined as the main set controls plus the double-blind baseline and OLE baseline values for subjects treated with placebo during the double-blind period who entered the OLE. This set will be an additional set used with the OLE Gant All Gant exposure mITT to add further long-term follow-up given that the two timepoints will differ by over four years for subjects added to this control group.

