5.4.6. CONTROLS APPLIED TO INDIVIDUAL ANALYSIS POPULATIONS

Controls will be applied to the three mITT populations as follows, with the exception that Mixed Model for Repeated Measures (MMRM) analyses will be assessed against the internal set controls (when any controls are used) and parameters which are not assessed within DIAN-OBS will be assessed against the internal set controls:

- OLE Gant mITT: Evaluated against main set controls
- OLE Gant All Gant exposure mITT: Evaluated against main set controls (as primary set of controls) and also against extended set controls (as supportive set of controls)
- All Gant exposure mITT: Evaluated against main set controls

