16.2.3. PRIMARY ANALYSIS OF KEY SECONDARY EFFICACY VARIABLES

16.2.3.1. Primary Analysis of CDR-SB

The primary analysis will be on the All Gant Exposure mITT, with other baseline covariates (such as baseline EYO) defined in the same way as baseline for the associated population. The recurrent progression is defined as any progression which is either the first increase in CDR-SB above baseline or any progression above the highest preceding post-baseline value identified as a progression, where progression above the preceding value must be observed at two consecutive measurements unless the progression occurs at the last measurement. Subjects without a progression event at their last measurement will be censored at the time of that measurement. The time-to-event is the time elapse between the two visits where the recurrent progression is observed, or the time since the baseline assessment for the first progression. Subjects can contribute multiple records to the analysis (i.e., once for each progression and potentially for censoring at the time of last measurement). The same definition will be applied to all controls as defined in [Section 5.4](#). The Cox proportional hazards model employing the Andersen-Gill method (Prentice RL, 1981) with robust variance estimator will be used to compare the hazards of recurrent progression in CDR-SB between population and all controls. The model will include treatment group and baseline EYO as the fixed effects. Should the model produce a two-sided p-value less than 0.10, a sensitivity analysis will be conducted using the shared frailty method (add reference).

Author: [REDACTED]

Version Number:

7

Version Date:

07Dec2023

Template No.: CS_TP_BS016 Revision 6

Reference: CS_WI_BS005

Effective Date: 02Dec2019

Analyses will be conducted separately for baseline asymptomatic and symptomatic subjects.

The same analysis will be applied to the OLE Gant mITT population and the OLE Gant All Gant exposure mITT populations, along with all controls. The analysis will also be conducted for each of the three mITT populations based on the baseline asymptomatic and symptomatic subjects presented separately. A Kaplan-Meier figure will be generated for baseline asymptomatic subjects for all three mITT populations and associated controls.

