16.2.3.2. Primary Analysis of CDR Global

The primary analysis will be on the All Gant Exposure mITT, with all the other baseline covariates (such as baseline EYO) defined in the same way as baseline for the associated population. The time to the first disease progression is defined as the time from the baseline to the first visit where CDR Global is greater than CDR Global baseline value, where a progression is considered an increase above baseline observed at two consecutive measurements unless the progression occurs at the last measurement. Subject without progression will be censored at their last measurement.

The Cox proportional hazards model will be applied to compare the hazards of disease progression in CDR Global between each of the three mITT population separately and all

Author: [REDACTED]

Version Number:

7

Version Date:

07Dec2023

Template No.: CS_TP_BS016 Revision 6

Reference: CS_WI_BS005

Effective Date: 02Dec2019

controls. The models will include the treatment group (specifically gantenerumab and controls) and baseline EYO as the fixed effects.

Analyses will be conducted separately for baseline asymptomatic and symptomatic subjects. A Kaplan-Meier figure will be generated for baseline asymptomatic subjects for all three mITT populations and associated controls.

Spaghetti plot of EYO for each participant will be presented for each of the three mITT populations. Lines and data points will be coded by different color/symbol for different CDR groups (without progression, with progression) and doses. This figure will be generated by Washington University team.

16.2.3.3. Primary Analysis of OLE Cognitive Composite, FAS, MMSE, Tau-PET SUV, CSF NfL and CSF MTBR243

The annual disease progression between the OLE Gant mITT population and all controls (with the exception of internal controls only for Tau-PET SUV) will be compared using a linear mixed effects (LME) model. CSF NfL will be log transformed for the analysis. The LME model will include time since baseline (in years: treated as continuous), treatment group (the OLE Gant mITT and all control), interaction between the treatment group and time, and random intercepts and slopes for each subject as the random effects. The unstructured covariance will be used to model the covariance between random intercepts and random slopes and will be modelled separately for baseline asymptomatic and symptomatic subjects.

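### Extended set controls keep only two values per placebo OLE entrant, which biases the supportive Cox comparisons for the OLE Gant All Gant exposure mITT

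*SAP*

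**What the plan says.** SAP 5.4.4 adds to the main set controls "the double-blind baseline and OLE baseline values for subjects treated with placebo during the double-blind period who entered the OLE", and notes that "the two timepoints will differ by over four years for subjects added to this control group". SAP 5.3 repeats the rule ("using DB and OLE baseline values for double-blind placebo subjects entering OLE"). The stated purpose is to add long-term follow-up.

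SAP 5.4.6 assigns this set to one population. The OLE Gant All Gant exposure mITT is evaluated against the main set as its primary controls, and (SAP 5.4.6, "also against extended set controls (as supportive set of controls").

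Two Cox analyses reach this population:

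- **CDR-SB, recurrent progression (SAP 16.2.3.1).** After specifying the model for the All Gant exposure mITT, the SAP says "The same analysis will be applied to the OLE Gant mITT population and the OLE Gant All Gant exposure mITT populations, along with all controls". A participant may contribute several progressions.
- **CDR Global, first progression (SAP 16.2.3.2).** Time to event is "defined as the time from the baseline to the first visit where CDR Global is greater than CDR Global baseline value". The model is run for each of the three mITT populations against controls.

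Both sections require a rise to be seen at two consecutive measurements, and both waive this at the last measurement. Neither treats the added controls as interval-censored or leaves them out.

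On the schedule, Protocol 3.5 lists "Clinical measures to be obtained at the CRI Entry, baseline (V2), and annual visits for both the CRI period and treatment periods", and CDR is among those measures.

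**The concern.** Placebo participants who did not enter the OLE contribute their double-blind placebo data without restriction (SAP 5.4.3 with 5.4.2). Those from the same arm who did enter are cut to a first and a last value. With one post-baseline value:

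- a participant who worsened at several annual visits is counted once;
- a rise at Year 1 is dated at OLE baseline, more than four years after double-blind baseline;
- that value is also the last measurement, so confirmation is always waived.

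The added controls therefore sit in the risk set for years with no possibility of an event, and then have several years' worth of events on one date. Hazards are non-proportional because of the visits kept, whatever the drug does.

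The extended set is the only control set that includes placebo OLE entrants. The internal controls are placebo participants who did not continue. If the two sets give different hazard ratios, a reader could not tell whether the added participants progressed differently or the missing visits caused the difference.

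**Working it through.** The documents give no event count, power or expected hazard ratio for this comparison, so there is no stated figure to reproduce.

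**Inputs from the documents**

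- Placebo carriers 40 and gantenerumab carriers 52 in the double-blind period (Protocol 3.3).
- OLE recruitment goal 60 to 90 of 144 (Protocol Appendix 3, 4.1.2).
- Gap between the two values over four years (SAP 5.4.4); participants "committed as much as 4 to 7 years to the double-blind treatment period" (Protocol Appendix 3, 1.9.2).

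**Assumptions**

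- OLE entry proportional to arm size. Placebo entrants: 60 × 40/144 = 16.7 to 90 × 40/144 = 25, midpoint about 21. Gantenerumab entrants: 60 × 52/144 = 21.7 to 90 × 52/144 = 32.5, midpoint about 27. Internal controls: 40 − 21 = 19.
- Progression rate λ of 0.10 to 1.0 per year; external controls 0 to 150; annual visits; OLE baseline at year 5 to 7. None of these is given for this comparison.

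**Step 1: events lost and dated late.** Let CDR-SB steps arrive at rate λ per year and persist. Expected counted progressions over T years are T(1 − e^(−λ)) with annual visits, and 1 − e^(−λT) with a baseline and one value at T. For T = 5:

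| λ per year | Annual visits | Two values | Ratio |
|---|---|---|---|
| 0.1 | 5(1 − e^−0.1) = 0.48 | 1 − e^−0.5 = 0.39 | 0.83 |
| 0.3 | 1.30 | 0.78 | 0.60 |
| 0.6 | 2.26 | 0.95 | 0.42 |
| 1.0 | 3.16 | 0.99 | 0.31 |

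Over this range of λ, a first progression is dated on average 2.2 to 3.5 years late when T = 5, 1.6 to 2.5 years when T = 4, and 3.4 to 5.4 years when T = 7.

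**Step 2: effect on the first-progression hazard ratio, no drug effect.** Simulated Cox models with treatment as the only covariate, 19 internal controls, 21 two-value entrants, and 27 or 30 gantenerumab participants:

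| λ per year | 50 to 150 external controls, two values |
|---|---|
| 0.10 to 0.15 | about 0.89 to 0.97 |
| 0.25 | 1.04 to 1.14 |
| 0.6 | 1.2 to 1.6 |

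With all visits kept, the hazard ratio is about 0.97 to 1.02; single cells ranged from 0.96 to 1.03. Simulation error is a few hundredths, so the slow-progression bias is small and the fast-progression bias is clear. The upper part of the 1.2 to 1.6 range comes from Efron handling of ties; Breslow handling gives 1.50 with 50 external controls and 1.23 with 150.

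**Step 3: recurrent CDR-SB, no drug effect.** Two-value hazard ratios with 50 and 150 external controls:

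| λ per year | Gap time | Time since baseline |
|---|---|---|
| 0.15 | 1.01, 0.96 | 0.94, 0.93 |
| 0.6 | 1.25, 1.10 | 1.18, 1.07 |

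**Step 4: a real effect.** At a true rate ratio of 0.5 and λ = 0.6, with 50 and 150 external controls, the two-value set gives 0.72 and 0.64 (recurrent, gap time) and 0.81 and 0.70 (first progression). The main set gives 0.57 to 0.58, and keeping all visits gives 0.56 to 0.58.

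**Why the sign changes.** Years of forced zero hazard dilute the control hazard early and push the ratio against gantenerumab. The pile-up of events at OLE baseline pushes the other way. With fast progression, losing and delaying events dominates. With slow progression, few events are lost and the late cluster carries weight.

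**The case against.** The strongest reply is about reach. The extended set is supportive, and it serves one population. That population is not primary either: CDR-SB and CDR Global are analysed primarily in the All Gant exposure mITT, which uses main set controls only, and the interim primaries also use the main set (SAP 17). The primary PiB-PET model has no controls (SAP 16.1.3). The SAP's change log adds that the OLE ended early and the study report will be abbreviated. All of this stands.

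The SAP's stated aim is long-term follow-up, and two widely spaced values are less of a problem for the LME slopes. That also stands; the defect is specific to the time-to-event analyses.

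A reader might infer a serious inflation of false-positive efficacy claims. With no external controls and a rate of 0.25 per year, the simulated null hazard ratio is about 1.4 and two-sided rejection about 21 to 24%. The documents do not support that reading. The extended set contains the main set, which includes external controls by definition (SAP 5.4.3). With 50, 100 and 150 external controls, rejection at that rate is about 11%, 8% and 8%. In the cell with no external controls, 23.7 of 24 percentage points were rejections against gantenerumab. Across rates of 0.10 to 0.25, false benefit never exceeded 4.5%, against a nominal 2.5% per side.

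Two further limits stand. The simulations omit the EYO covariate and the separate asymptomatic and symptomatic fits. Because simulated steps persist, they also do not test the confirmation waiver. And annual double-blind CDR is inferred from current platform text; the double-blind visit schedules are in earlier amendments that are not in hand.

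**Conclusion.** The point holds in a limited form. As written, the extended set biases the supportive Cox hazard ratios for the OLE Gant All Gant exposure mITT in the absence of any drug effect, because added controls can have only one progression, dated at OLE baseline and unconfirmed. That much follows from the text alone.

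The size depends on progression rates and the number of external controls, which the documents do not give. Fast progression, as might be expected in the symptomatic analyses, biases against gantenerumab and could mask part of a real benefit. Slow progression biases slightly in its favour.

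It would be wrong to infer that any primary conclusion is compromised. The main-set comparisons, the primary PiB-PET analysis and the primary CDR analyses do not use this set. The point should be corrected, but it is not critical.

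**What to change.** In SAP 5.4.4, and in the matching text in 5.3, define the extended set controls for the time-to-event analyses as the main set controls plus all available double-blind CDR visits through OLE baseline for placebo participants who entered the OLE, censored at OLE baseline. Apply the same progression and confirmation rules to them as to everyone else. Nothing is counted twice, because the treated side of this population contains only participants on gantenerumab in both periods (SAP 5.3).

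The edit is short and uses data the trial should already hold. The cost is a documented change to a supportive analysis after the interim, with a stated reason. The two-value version can stay for the LME models, or be reported alongside so that the effect of the change is visible.

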5.4.5. CONCURRENT CONTROLS

Subjects in any control group will be identified as either concurrent or non-concurrent controls. The concurrent set of controls are defined as the internal set controls (including those in the extended set controls where applicable) and the external set controls where the point of eligibility occurs on or after the first dose of double-blind treatment in DIAN-TU-001. Based on this convention, the subject's baseline visit for internal set controls or point of eligibility for external

Author: [REDACTED]

Version Number:

7

Version Date:

07Dec2023

Template No.: CS TP BS016 Revision 6

Reference: CS WI BS005

Effective Date: 02Dec2019

set controls will have occurred within the period during which DIAN-TU-001 subjects were treated (including the gap period between double-blind and open-label treatment).

5.4.6. CONTROLS APPLIED TO INDIVIDUAL ANALYSIS POPULATIONS

Controls will be applied to the three mITT populations as follows, with the exception that Mixed Model for Repeated Measures (MMRM) analyses will be assessed against the internal set controls (when any controls are used) and parameters which are not assessed within DIAN-OBS will be assessed against the internal set controls:

- OLE Gant mITT: Evaluated against main set controls
- OLE Gant All Gant exposure mITT: Evaluated against main set controls (as primary set of controls) and also against extended set controls (as supportive set of controls)
- All Gant exposure mITT: Evaluated against main set controls

5.5. SAFETY ANALYSIS SET [SAF]

The safety analysis population includes all subjects who have consented to participate and have received at least one dose of study drug in the gantenerumab OLE period.

6. GENERAL CONSIDERATIONS

All statistical analyses and summary information are to be generated according to this SAP. Any deviations from this SAP will be documented in the CSR.

For continuous variables, descriptive statistics such as the number of subjects (n), mean, standard deviation (SD) or standard error (SE), minimum, median, and maximum values will be reported. Lower and upper quartiles will be presented for select efficacy summaries. For categorical

variables, frequencies and percentages will be displayed. Subject data collected in the electronic case report form (eCRF) and other data sources will be presented in listings.

6.1. REFERENCE START DATE AND STUDY DAY

Study Day will be calculated from the reference start date and will be used to show start/stop day of assessments and events.

Reference start date is defined as the day of the first dose of OLE study medication (where Day 1 is the day of the first dose of study medication) and will appear in every listing where an assessment date or event date appears.

If the date of the event is on or after the reference date, then:

Study Day = (date of event – reference date) + 1.

If the date of the event is prior to the reference date, then:

Study Day = (date of event – reference date).

In the situation where the event date is partial or missing, Study Day and any corresponding durations will appear partial or missing in the listings.

Similar variables will be created where needed for analysis based on using a reference start date as the day of first double-blind treatment. Study day will also be created for all controls where the reference date corresponds to the date of the visit to be used as the analysis baseline.

Author: [REDACTED]

Version Number:

7

Version Date:

07Dec2023

Template No.: CS_TP_BS016 Revision 6

Reference: CS_WI_BS005

Effective Date: 02Dec2019

